#### 7.6 Criteria for Removal from Protocol Treatment

- a. Recurrence of disease or symptomatic deterioration (as defined in [Section 10.0](#)). If the patient has documented recurrence as defined in [Section 10.1](#), unblinding of study treatment as outlined in [Section 7.5](#) may be requested.
- b. Unacceptable toxicity defined as any toxicity requiring discontinuation of study drug per [Section 8.0](#). If a patient is removed from protocol treatment due to toxicity, he/she must continue to be followed for recurrence according to the same schedule as detailed in [Sections 7.2](#) and [9.0](#) (every 4 months [18 weeks] during Year 1 (regardless whether patient is still on active protocol treatment), then every six months for Years 2 and 3, and then annually thereafter until recurrence, death, or 10 years after registration, whichever comes first. Recurrence assessments consist of physical exams and CT scans)
- c. Delay in protocol treatment > 21 days due to pneumonitis or > 28 days due to any other reason. If a patient is removed from protocol treatment due to toxicity, the must continue to be followed for recurrence according to the same schedule as detailed in [Sections 7.2](#) and [9.0](#) (every 4 months [18 weeks] during Year 1 (regardless whether patient is still on active protocol treatment), then every six months for two years, and then annually thereafter until recurrence, death, or 10 years after registration, whichever comes first. Recurrence assessments consist of physical exams and CT scans)
- d. Completion of nine cycles of protocol treatment.
- e. The patient may withdraw from the study at any time for any reason.

#### 7.7 Discontinuation of Treatment

All reasons for discontinuation of treatment must be documented in the study forms.

#### 7.8 Follow-Up Period

All patients will be followed for a maximum of 10 years after registration or until death (whichever occurs first) for recurrence and survival.

## 8.0 DOSE MODIFICATIONS

### 8.1 NCI Common Terminology Criteria for Adverse Events

This study will utilize the CTCAE (NCI Common Terminology Criteria for Adverse Events) Version 4.0 for toxicity and Serious Adverse Event reporting. A copy of the CTCAE Version 4.0 can be downloaded from the CTEP home page (<http://ctep.cancer.gov>). All appropriate treatment areas should have access to a copy of the CTCAE Version 4.0.

### 8.2 General Dose Modification Considerations

- a. Missed doses are to be omitted rather than made up.
- b. If multiple toxicities are experienced, dose modifications will be based on the toxicity requiring the largest dose reduction.

- c. Reductions are based on the dose given in the preceding cycle and are based on toxicities observed since the prior toxicity evaluation.
- d. Once dose is reduced, patients will continue at new dose. No dose re-escalations are allowed.
- e. If protocol treatment is held > 21 days for pneumonitis or > 28 days due to any other reason, patient should be removed from protocol treatment.

8.3 Everolimus Dose Levels

Dose Levels	Dose
Full	10 mg daily (two 5 mg tablets)
-1 Level	5 mg daily
-2 Level	5 mg every other day
-3 Level	Discontinue study drug

8.4 Everolimus Dose Modifications

**NOTE: NO DOSE ESCALATION OR RE-ESCALATION IS ALLOWED.**

Toxicity	Actions
Non-hematological toxicity	
Grade 2 (except pneumonitis – see 8.4.c ) (except hyperlipidemia – see 8.4.b )*	If the toxicity is tolerable to the patient, maintain the same dose. If the toxicity is intolerable to patient, interrupt everolimus until recovery to Grade ≤ 1. Then reintroduce everolimus at same dose. If event returns to Grade 2, then interrupt everolimus until recovery to Grade ≤ 1. Then reintroduce everolimus at one lower dose level.
Grade 3 (except pneumonitis – see 8.4.c ) (except hyperlipidemia – see 8.4.b )*	Interrupt everolimus until recovery to Grade ≤ 1. Then reintroduce everolimus at one lower dose level. For pneumonitis consider the use of a short course of corticosteroids.
Grade 4	Discontinue everolimus.
Hematological toxicity	
Grade 2 Thrombocytopenia (platelets < 75, ≥ 50x10  /L)	Interrupt everolimus until recovery to Grade ≤1 (≥ 75 x10  /L). Then reintroduce everolimus at same dose. If thrombocytopenia again returns to Grade 2, interrupt everolimus until recovery to Grade ≤1. Then reintroduce everolimus at one lower dose level.
Grade 3 Thrombocytopenia (platelets < 50, ≥ 25x10  /L)	Interrupt everolimus until recovery to Grade ≤ 1 (platelets ≥ 75 x10  /L). Then resume everolimus at one lower dose level. If Grade 3 thrombocytopenia recurs, discontinue everolimus.
Grade 4 Thrombocytopenia (platelets < 25 x10  /L)	Discontinue everolimus.

Toxicity	Actions
Non-hematological toxicity	
Grade 3 Neutropenia (neutrophils < 1, $\geq 0.5 \times 10^9/L$ )	Interrupt everolimus until recovery to Grade $\leq 1$ (neutrophils $\geq 1.5 \times 10^9/L$ ). Then resume everolimus at the same dose. If ANC again returns to Grade 3, hold everolimus until the ANC $\geq 1.5 \times 10^9/L$ . Then resume everolimus at one lower dose level. Discontinue patient from study therapy for a third episode of Grade 3 neutropenia.
Grade 4 Neutropenia (neutrophils < $0.5 \times 10^9/L$ )	Interrupt everolimus until recovery to Grade $\leq 1$ (neutrophils $\geq 1.5 \times 10^9/L$ ). Then resume everolimus at one lower dose level. If Grade 3 or Grade 4 neutropenia occurs despite this dose reduction, discontinue everolimus.
Grade 3 febrile neutropenia (not life-threatening)	Interrupt everolimus until resolution of fever and neutropenia to Grade $\leq 1$ . Hold further everolimus until the ANC $\geq 1,500/mm^3$ and fever has resolved. Then resume everolimus at one lower dose level. If febrile neutropenia recurs, discontinue everolimus.
Grade 4 febrile neutropenia (life-threatening)	Discontinue everolimus.

\* Grade 2-3 hyperlipidemia (hypercholesterolemia and/or hypertriglyceridemia) should be managed using medical therapies (see [Section 8.4b](#)).

If a patient requires a dose delay of > 21 days for pneumonitis or > 28 days for any other reason from the intended day of the next scheduled dose, then the patient must be removed from the protocol treatment.

a. Hematological Toxicity

No dose adjustments are recommended for anemia. The treating physician may hold everolimus for anemia if it is felt to be in the best interest of the patient. Aranesp (darbepoetin alfa) and Procrit (epoetin alfa) are not indicated for anemia. If patient does not recover after 28 days of holding drug then the patient must be removed from treatment.

Growth factors (e.g. G-CSF, GM-CSF, erythropoietin, platelet growth factors, etc.) are not to be administered prophylactically but may be prescribed by the treating physician for rescue from severe hematologic events.

b. Hyperlipidemia and Hyperglycemia

Treatment of hyperlipidemia should take into account the pre-treatment status and dietary habits. Blood tests to monitor hyperlipidemia must be taken in the fasting state. Grade 2 or greater hypercholesterolemia (> 300 mg/dL or 7.75 mmol/L) or Grade 2 or greater hypertriglyceridemia (> 300 mg/dL - 500 mg/dL; >3.42 mmol/L- 5.7 mmol/L) should be treated with a 3-hydroxy-3-methyl-glutaryl (HMG)-CoA reductase inhibitor (e.g., atorvastatin, pravastatin) or appropriate lipid-lowering medication, in addition to diet. Patients should be monitored clinically and through serum biochemistry for the development of rhabdomyolysis and other adverse events as required in the product label/data sheets for HMG-CoA reductase inhibitors.

Note: Concomitant therapy with fibrates and an HMG-CoA reductase inhibitor is associated with an increased risk of a rare but serious skeletal muscle toxicity manifested by rhabdomyolysis, markedly elevated creatine phosphokinase (CPK) levels and myoglobinuria, acute renal failure and sometimes death. The risk

versus benefit of using this therapy should be determined for individual patients based on their risk of cardiovascular complications of hyperlipidemia.

Grade 3 hyperglycemia has been observed in patients receiving everolimus therapy. The fasting state of patients should be verified when interpreting results. It is suggested that optimal glucose control should be achieved before starting a patient on everolimus and should be monitored during everolimus therapy.

c. Pneumonitis

Pneumonitis is a recognized adverse effect of rapamycins (sirolimus, temsirolimus, and everolimus). Numerous case reports in the literature suggest that rapamycin-associated pneumonitis is relatively unaggressive, limited in extent, and reversible upon drug discontinuation. The term 'pneumonitis' is used here to describe non-infectious, non-malignant infiltration in the lungs which is evident radiologically. More precise diagnosis should follow histocytological examination following lung biopsy, generally during bronchoscopy which may or may not be symptomatic.

Both asymptomatic and symptomatic non-infectious pneumonitis have been noted in patients receiving everolimus. A diagnosis of non-infectious pneumonitis should be considered in patients presenting with non-specific respiratory signs and symptoms such as hypoxia, pleural effusion, cough or dyspnea, and in whom infectious, neoplastic and other non medical causes have been excluded by means of appropriate investigations. Patients should be advised to report promptly any new or worsening respiratory symptoms.

In order to monitor for asymptomatic non-infectious pneumonitis, the regularly scheduled chest CTs for disease surveillance should be assessed for evidence of pneumonitis during protocol treatment. Additional chest CT scans may be performed, when clinically necessary. If non-infectious pneumonitis develops, a consultation with a pulmonologist should be considered.

Management of Non-Infectious Pneumonitis

Worst Grade Pneumonitis	Required Investigations	Management of Pneumonitis	Everolimus Dose Adjustment
Grade 1	CT scans with lung windows and pulmonary function testing including: spirometry, DLCO, and room air O 2 saturation at rest. Repeat chest x-ray/CT scan every 2 Cycles until return to baseline.	No specific therapy is required	Administer same dose of everolimus.
Grade 2	CT scan with lung windows and pulmonary function testing including: spirometry, DLCO, and room air O 2 saturation at rest. Repeat each subsequent Cycle until return to baseline. Consider bronchoscopy	Symptomatic only. Prescribe corticosteroids if cough is troublesome.	Reduce everolimus one dose level until recovery to ≤ Grade 1. Everolimus may also be interrupted if symptoms are troublesome.

Worst Grade Pneumonitis	Required Investigations	Management of Pneumonitis	Everolimus Dose Adjustment
	*		Patients will be removed from protocol treatment if they fail to recover to $\leq$ Grade 1 within 21 days.
Grade 3	CT scan with lung windows and pulmonary function testing including: spirometry, DLCO, and room air O 2 saturation at rest. Repeat each subsequent Cycle until return to baseline. Bronchoscopy is recommended *	Prescribe corticosteroids if infective origin is ruled out. Taper as medically indicated.	Hold treatment until recovery to $\leq$ Grade 1. May restart protocol at one lower dose level. Patients will be removed from protocol treatment if they fail to recover to $\leq$ Grade 1 within 21 days.
Grade 4	CT scan with lung windows and required pulmonary function testing includes: spirometry, DLCO, and room air O 2 saturation at rest. Repeat each subsequent Cycle until return to baseline. Bronchoscopy is recommended *.	Prescribe corticosteroids if infective origin is ruled out. Taper as medically indicated.	Discontinue treatment.

---

\*A bronchoscopy with biopsy and/or bronchoalveolar lavage is recommended.

d. Oral Mucositis

In addition to the dose modifications for non-hematological toxicity outlined in [Section 8.4](#), oral mucositis due to everolimus should be treated using local supportive care. Follow the paradigm below for treatment of oral mucositis:

1. For mild toxicity (Grade 1), use conservative measures such as non-alcoholic mouth wash or salt water (0.9%) mouth wash several times a day until resolution.
2. For more severe toxicity (Grade 2 in which case patients have pain but are able to maintain adequate oral alimentation, or Grade 3 in which case patients cannot maintain adequate oral alimentation), the suggested treatments are topical analgesic mouth treatments (i.e., local anesthetics such as benzocaine, butyl aminobenzoate, tetracaine hydrochloride, menthol, or phenol) with or without topical corticosteroids, such as triamcinolone oral paste 0.1% (Kenalog in Orabase®).

3. Agents containing hydrogen peroxide, iodine, and thyme derivatives may tend to worsen mouth ulcers. It is preferable to avoid these agents.
4. Antifungal agents must be avoided unless a fungal infection is diagnosed. In particular, systemic imidazole antifungal agents (ketoconazole, fluconazole, itraconazole, etc.) should be avoided in all patients due to their strong inhibition of everolimus metabolism, thereby leading to higher everolimus exposures. Therefore, topical antifungal agents are preferred if an infection is diagnosed. Similarly, antiviral agents such as acyclovir should be avoided unless a viral infection is diagnosed.

e. Nausea

Routine premedication for nausea is not necessary, but symptomatic patients should be treated with standard anti-nausea/antiemetic therapy as necessary.

If the patient vomits after taking the tablets, the dose is replaced only if the tablets can actually be seen and counted.

f. Diarrhea

Diarrhea has been seen with everolimus. In general, diarrhea has been transient, usually not of sufficient severity to hinder administration of everolimus and responsive to loperamide. The recommended dose of loperamide is 4 mg at first onset, followed by 2 mg PO q 2-4 hours until diarrhea free for 12 hours.

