	Nausea		Nausea (Gr 2)
	Vomiting		Vomiting (Gr 2)
GENERAL DISORDERS AND ADMINISTRATION SITE CONDITIONS			
	Edema limbs		Edema limbs (Gr 2)
Fatigue			Fatigue (Gr 2)
	Fever		Fever (Gr 2)
INFECTIONS AND INFESTATIONS			
	Infection 		Infection (Gr 2)

Adverse Events with Possible Relationship to Everolimus (RAD-001) (CTCAE 4.0 Term) [n= 3033]			Specific Protocol Exceptions to Expedited Reporting (SPEER)
Likely (>20%)	Less Likely (<=20%)	Rare but Serious (<3%)	
INJURY, POISONING AND PROCEDURAL COMPLICATIONS			
		Wound complication 	
INVESTIGATIONS			
	Alanine aminotransferase increased		Alanine aminotransferase increased (Gr 2)
	Alkaline phosphatase increased		Alkaline phosphatase increased (Gr 2)
	Aspartate aminotransferase increased		Aspartate aminotransferase increased (Gr 2)
	Cholesterol high		Cholesterol high (Gr 2)
	Creatinine increased		Creatinine increased (Gr 2)
	Lymphocyte count decreased		Lymphocyte count decreased (Gr 2)
	Neutrophil count decreased		Neutrophil count decreased (Gr 2)
	Platelet count decreased		Platelet count decreased (Gr 2)
	Weight loss		
	White blood cell decreased		White blood cell decreased (Gr 2)
METABOLISM AND NUTRITION DISORDERS			
	Anorexia		Anorexia (Gr 2)
	Hyperglycemia 		Hyperglycemia (Gr 2)
	Hypertriglyceridemia		Hypertriglyceridemia (Gr 2)
	Hypophosphatemia		Hypophosphatemia (Gr 2)
MUSCULOSKELETAL AND CONNECTIVE TISSUE DISORDERS			
	Arthralgia		
	Back pain		
	Pain in extremity		
NERVOUS SYSTEM DISORDERS			
	Dysgeusia		
	Headache		Headache (Gr 2)
RENAL AND URINARY DISORDERS			
		Acute kidney injury	
RESPIRATORY, THORACIC AND MEDIASTINAL DISORDERS			
	Cough		Cough (Gr 2)

Adverse Events with Possible Relationship to Everolimus (RAD-001) (CTCAE 4.0 Term) [n= 3033]			Specific Protocol Exceptions to Expedited Reporting (SPEER)
Likely (>20%)	Less Likely (<=20%)	Rare but Serious (<3%)	
	Dyspnea		Dyspnea (Gr 2)
	Epistaxis		Epistaxis (Gr 2)
	Pneumonitis 		
SKIN AND SUBCUTANEOUS TISSUE DISORDERS			
	Dry skin		
	Pruritus		
Rash maculo-papular			Rash maculo-papular (Gr 2)
		Skin and subcutaneous tissue disorders - Other (angioedema) 	

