## 7.0 TREATMENT PLAN

For treatment or dose modification related questions, please contact [name] at [name] or [name] at [name]. For dosing principles or questions, please consult the SWOG Policy #38 "Dosing Principles for Patients on Clinical Trials" at <http://swog.org> (then click on "Policies and Manuals" under the "Visitors" menu and choose Policy #38).

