#### Most Prevalent Grade 2-4 Adverse Events in the Everolimus Arm of EVEREST

Among all Randomized Patients on the Everolimus Arm Who Received Any Study Drug

Toxicity	% of Evaluable with Grade 2-4
High Cholesterol	10%
Fatigue	19%
Hyperglycemia	14%
Hypertriglyceridemia	27%
Oral mucositis	35%
Rash	14%
Composite Endpoints	
Any Toxicity Grade 2-4	87%
Any Toxicity Grade 3-4	46%
Refusal/Tox within first 3 months	25%
Refusal/Tox within first 6 months	41%
Refusal/Tox prior to 12 months	52%

In order to simplify power calculations related to everolimus blood concentrations, we will assume the distribution of values will be divided into quartiles. The following table indicates the minimally detectable odds ratio that could be detected between the lowest and highest quartile in terms of predicting an adverse event. A range of prevalences are illustrated below to show how the effect size changes with the prevalence of the adverse event.

Minimally Detectable Odds Ratio for Highest versus Lowest Quartile of everolimus in the blood, assuming 80% Statistical Power and a Two-sided Alpha=0.05.

	Prevalence of Adverse Event Endpoint				
	10%	20%	30%	40%	50%

Q4 vs. Q1 of everolimus concentration	6.5	3.6	3.0	2.7	2.7
---------------------------------------	-----	-----	-----	-----	-----

An individual adverse event that is only reported by 10% of patients who receive everolimus will need to have a very strong association with concentration of everolimus in the blood (odds ratio 6.5 between highest and lowest concentration) in order to be detected as a significant association. An association of any Grade 3-4 toxicity only needs to be in the range of an odds ratio of 2.7 to be detectable.

For patients who have had a dose reduction of protocol therapy at the time of their blood draw, we will handle this in two ways. First, we will just analyze the everolimus level as it appears in the blood and ignore the dose received, and the second approach will standardize the amount of everolimus in the blood conditional on the dose of drug taken.

Logistic regression will be used to model adverse event outcomes with everolimus blood concentration as a predictor, adjusting for other stratification factors and age, gender and race.

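### Section 8.4: after two Grade 3 neutropenia episodes, a third at Grade 3 ends treatment, but a Grade 4 episode, read literally, leads to a restart at a lower dose

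*Combined protocol and SAP*

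**What the plan says.** Section 8.3 gives three active dose levels: 10 mg daily, 5 mg daily (level -1) and "5 mg every other day" (level -2). The next step down, level -3, is discontinuation.

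Section 8.4 has separate rows for neutropenia without fever:

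- **Grade 3** (neutrophils 0.5 to below 1.0 x10^9/L). After the first episode, hold until at least 1.5 x10^9/L and resume at the same dose. After the second, hold and resume one level lower. The row ends: "Discontinue patient from study therapy for a third episode of Grade 3 neutropenia".
- **Grade 4** (below 0.5 x10^9/L). Hold until at least 1.5 x10^9/L. "Then resume everolimus at one lower dose level. If Grade 3 or Grade 4 neutropenia occurs despite this dose reduction, discontinue everolimus".

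Febrile neutropenia has its own rows. At Grade 3 the dose drops one level and a stop rule follows: "If febrile neutropenia recurs, discontinue everolimus". At Grade 4 the drug is stopped at once.

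Section 8.2 adds general rules. Where several toxicities occur, the one needing the largest reduction governs. Reductions start from the dose given in the preceding cycle. If treatment is "held > 21 days for pneumonitis or > 28 days due to any other reason, patient should be removed from protocol treatment".

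**The concern.** The Grade 3 row counts only Grade 3 episodes. The Grade 4 row looks only at what follows its own reduction. Neither row says what to do when a Grade 4 event follows two Grade 3 episodes, so the Grade 4 row applies as if neutropenia had not occurred before.

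A stop rule should not loosen as the event worsens. Section 8.5 warns that everolimus is immunosuppressive and that some infections under it have been severe and occasionally fatal. The patients are in an adjuvant setting after complete resection. At stake is re-exposure of a patient who has had two earlier Grade 3 episodes and a count below 0.5 x10^9/L on a reduced dose. No efficacy analysis is involved.

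**Working it through.** No statistical figure applies, so the check traces the rows of Section 8.4 through the dose levels of Section 8.3. G3 and G4 are episodes without fever, each recovering within the permitted hold, and no other toxicity changes the dose.

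**Starting from 10 mg daily**

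| History | Result |
|---|---|
| G3 | 10 mg daily |
| G3, G3 | 5 mg daily |
| G3, G3, G3 | stop |
| G3, G3, G4 | 5 mg on alternate days |
| G3, G4 | 5 mg daily |
| G3, G4, G3 | stop |
| G3, G4, G4 | stop |
| G4 | 5 mg daily |
| G4, G3 | stop |
| G4, G4 | stop |

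Four three-episode histories can be reached. Three end in discontinuation and one, G3-G3-G4, does not. This counts sequences; it is not a frequency. At the third episode, a count of 0.6 x10^9/L ends treatment and a count of 0.4 x10^9/L does not. After G3-G3-G4, any further G3 or G4 stops the drug.

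**Starting lower.** From 5 mg daily, G3-G3 already leads to alternate-day dosing, so a G4 event reaches level -3, which is discontinuation. No inversion arises there, or from a start on alternate days.

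**Whether other text resolves it**

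- The rule in Section 8.2b is for several toxicities, not successive episodes of one toxicity at different grades.
- Section 8.2c takes the preceding dose as the base, which supports the step from 5 mg daily to alternate days.
- The Grade 4 row that discontinues outright is for non-hematological toxicity. The label above the neutropenia rows appears to be a repeated table header, and neutropenia has its own Grade 4 row.
- In the Grade 4 row, the reduction referred to is the one just made for the Grade 4 event.
- The thrombocytopenia rows show no such inversion: recurrent Grade 3 stops, and any Grade 4 stops.

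**Dose at restart.** 5 mg / 2 days = 2.5 mg per day; 2.5 / 10 = 25% of the starting dose.

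**How common.** The adverse event table in Section 3.1c places neutrophil decrease in its middle frequency column (20% or less). Neutropenia is absent from the Section 11.5 table headed "Most Prevalent Grade 2-4 Adverse Events in the Everolimus Arm of EVEREST", whose lowest individual entry is 10%. This suggests, without proving, that Grade 2-4 neutropenia was below that level. The inverted history needs three separate severe episodes in 54 weeks. The documents give no count of affected patients.

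**Whether dosing is over.** The December 2020 update in Section 11.2 allows 6 years of follow-up after last accrual and expects the final analysis in March 2022. March 2022 - 6 years = March 2016; adding 378 days of treatment gives mid-March to mid-April 2017. Using that update's September 2021 data-maturity date instead gives September 2015 and a last dose about six months earlier. Dosing is complete on either basis.

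**The case against.** The strongest reply is that the inversion needs the least cautious of several plausible readings. A clinician could count a Grade 4 event as at least a third Grade 3 episode, or take the Grade 4 row's stop clause to cover any earlier reduction for neutropenia. A count below 0.5 also passes back through the Grade 3 range before it reaches 1.5. Sites with doubts have a route in Section 7.0: "For treatment or dose modification related questions, please contact". Many would stop the drug. That stands as a reason to expect few restarts, but it is inference: the table followed as written gives the restart.

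The second reply is rarity. The patient must have a deeper nadir on 5 mg daily than on either earlier occasion at 10 mg daily. The study calendar in Section 9.0 schedules blood counts only once per six-week cycle, which makes three documented and recovered episodes harder to accumulate. This stands and keeps the point small.

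The third reply is that with dosing probably over, little can be acted on. This also stands in part. It limits the value of the correction to a record check and any reuse of the table, but does not make the rule right.

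A last reply concerns the remedy. A site that counts a febrile episode towards the third episode could, under the revised Grade 3 row, stop a patient with Grade 3 febrile, then G3, then G4. That is consistent with the current wording, under which the same site would already stop Grade 3 febrile, then G3, then G3.

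**Conclusion.** The concern holds as a minor defect. From a 10 mg start, two Grade 3 episodes without fever followed by a Grade 4 episode lead to 5 mg on alternate days, while a third Grade 3 episode ends treatment.

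The remaining risk is small. Restart requires neutrophils of at least 1.5 x10^9/L, a hold beyond 28 days ends treatment, the restart dose averages a quarter of the original, the next Grade 3 or 4 episode stops the drug, and life-threatening febrile neutropenia stops it outright. Sample size, alpha and power are unaffected.

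The conclusion rests on a literal reading of the two rows without fever, with no other dose reduction in play. The febrile rows are not judged, and this is not a claim that the neutropenia rows contain no other gap. The dosing dates are inferred, because the documents do not state when the last patient was treated.

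**What to change.** Check the treatment records for any patient who had two Grade 3 neutropenia episodes without fever and was restarted after a later Grade 4 episode.

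If the table is reused, make two edits in Section 8.4:

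1. In the last sentence of the Grade 3 row, let the third-episode stop apply to neutropenia of Grade 3 or Grade 4.
2. In the Grade 4 row, add an exception to the instruction to resume one level lower: if the dose has already been reduced under the Grade 3 row, discontinue.

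The second edit alone would close the gap; the first makes the two rows agree. With Grade 3 febrile episodes added and handled under their own rows, 9 two-episode and 18 three-episode histories can be reached from 10 mg. The edits change only one of these 27, G3-G3-G4, which becomes a stop. No history starting at a lower dose changes. If febrile episodes are also graded by neutrophil count and the strictest row applies, 3 of 24 three-episode histories change, each with two Grade 3 counts followed by a Grade 4 count.

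The cost is one record check and two short wording changes, with no added tests, visits or patients.

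### The Grade 2 pneumonitis cell in Section 8.4c gives the dose reduction an end point, which contradicts the ban on re-escalation in Section 8.2d and at the head of Section 8.4

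*Combined protocol and SAP*

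**What the plan says.** The Grade 2 row of the pneumonitis management table in Section 8.4c opens its dose instruction with "Reduce everolimus one dose level until recovery to" Grade 1 or less. It then adds "Everolimus may also be interrupted if symptoms are troublesome", and ends with the removal rule, "Patients will be removed from protocol treatment if they fail to recover to" Grade 1 or less within 21 days. It does not say what dose the patient takes once recovered.

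Two general statements bear on that dose. Section 8.2d reads "Once dose is reduced, patients will continue at new dose. No dose re-escalations are allowed". The note at the head of Section 8.4, which contains 8.4c, reads "NO DOSE ESCALATION OR RE-ESCALATION IS ALLOWED". Neither carves out pneumonitis.

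The Grade 3 row of the same pneumonitis table holds treatment until recovery and then says "May restart protocol at one lower dose level".

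**The concern.** A reduction that lasts until an event ends when the event occurs. On the plain wording of the cell, a patient who recovers to Grade 1 or less goes back to the earlier dose. Section 8.2d and the 8.4 note forbid that. A site therefore has one specific instruction and two general ones that point in opposite directions, with no statement of which prevails.

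What is at stake is dosing after a lung toxicity. Section 8.4c describes this toxicity as reversible once the drug is stopped. Under one reading the patient is re-exposed to the dose at which the toxicity appeared; under the other the patient stays on the lower dose. Two sites could treat identical patients differently and each cite the protocol.

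**Working it through.** The plan states no figure for this point, so there is none to reproduce. The check sets the rules side by side and then does a short dose calculation.

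**Step 1: how the tables handle recovery.** These are all the rows in the 8.4 and 8.4c tables that hold or reduce the drug, leaving out rows that simply continue or discontinue it.

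| Row | Action | Dose after recovery |
|---|---|---|
| Grade 2 non-hematological, not tolerated | hold | same dose; one level lower if it returns |
| Grade 3 non-hematological | hold | one level lower |
| Grade 2 thrombocytopenia | hold | same dose; one level lower if it returns |
| Grade 3 thrombocytopenia | hold | one level lower |
| Grade 3 neutropenia | hold | same dose; one level lower after a second episode |
| Grade 4 neutropenia | hold | one level lower |
| Grade 3 febrile neutropenia | hold | one level lower |
| Grade 3 pneumonitis | hold | one level lower |
| Grade 2 pneumonitis | reduce one level; hold optional | not stated |

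In the first eight rows, recovery or resolution ends a *hold*, and the text then names the restart dose, as in "Then reintroduce everolimus at one lower dose level". None of the eight raises a dose that had been reduced, so none conflicts with 8.2d. In the last row, recovery ends a *reduction*, and nothing follows.

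**Step 2: whether another row fills the gap.** The general Grade 2 and Grade 3 non-hematological rows of the 8.4 table exclude pneumonitis and send the reader to 8.4c. The restart doses in those rows therefore do not apply, and the 8.4c cell is the operative one.

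**Step 3: size of the difference.** Section 8.3 gives the levels as 10 mg daily, 5 mg daily, 5 mg every other day, then discontinuation.

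- First reduction: 10 mg daily to 5 mg daily. If the earlier dose returns, 10 / 5 = 2.
- Second reduction: 5 mg daily to 5 mg every other day, which averages 5 / 2 = 2.5 mg daily. If the earlier dose returns, 5 / 2.5 = 2.
- A patient already at 5 mg every other day has discontinuation as the next level, so the ratio does not apply there.

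The readings therefore differ twofold in dose at both steps. The difference is pharmacological only in the everolimus arm; in the placebo arm only the number or frequency of tablets changes.

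**Step 4: whether it can still affect this trial.** The December 2020 Update in Section 11.2 allows six years of follow-up after the last accrual and expects the final analysis in March 2022. Taking those six years to end by then, last accrual was about March 2022 − 6 years = March 2016. Adding the 54-week course of Section 7.2 puts the last dose at about spring 2017.

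**The case against.** The best defence is that the protocol already settles the dose. Section 8.2d is a general rule stated without exceptions, the capitalised note covers the whole of 8.4, and the cell never says to resume or raise the dose. Re-escalation is an inference from one word, set against two explicit prohibitions. The table's first column is also headed by the *worst* grade of pneumonitis, which recovery does not change, and this favours a lasting reduction. A Grade 3 patient needs a stated restart dose because the drug was stopped; a Grade 2 patient by default simply stays on the lower dose. Section 7.0 gives sites a contact for dose-modification questions.

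Most of this stands as evidence of intent, and the proposed wording adopts that intent. It does not repair the cell. The row still attaches an end point to the reduction, the 8.4 table sends pneumonitis out of its general rows to 8.4c, and a specific instruction is easily read as overriding a general one.

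A reader might go further and infer that the protocol deliberately permits re-escalation for pneumonitis. The documents do not support that: no exception is stated, and both bans are unqualified.

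**Conclusion.** The point holds as a wording conflict in an operative safety rule: the Grade 2 pneumonitis cell, read as written, contradicts 8.2d and the 8.4 note. The readings differ twofold in dose for an everolimus-arm patient who recovers from a Grade 2 episode at a reduced dose. Severity is minor. Power and the hazard ratio are unaffected, and dosing has probably ended, on the assumption that the six follow-up years run out by March 2022.

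Two stronger inferences should not be drawn.

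- **That the 21-day removal limit goes unchecked.** A reader might infer this because the row's tests carry the instruction "Repeat each subsequent Cycle until return to baseline" and a cycle is 6 × 7 = 42 days. But a rule that removes patients who have not recovered within 21 days already requires the grade to be known by then, and Section 7.6b makes toxicity requiring discontinuation a removal criterion. A later check would be a deviation, not something the plan allows. Cycle 1 also has weekly toxicity assessments and a Week 4 examination, and for onset in the second half of a later cycle the next cycle visit falls within 21 days.
- **That a cumulative excess dose can be stated.** Any total depends on when the episode occurs, whether the site disregards the ban, and whether the patient then completes treatment. Section 11.5 reports that 52% of everolimus patients stopped for refusal or toxicity before 12 months. Neither that table nor any other part of the documents gives a Grade 2 pneumonitis rate, so the number of patients affected cannot be estimated.

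**What to change.** In the Grade 2 dose cell of the Section 8.4c table, replace the first sentence with: *Reduce everolimus one dose level; do not re-escalate after recovery (8.2d).* Leave the optional interruption and the 21-day removal sentence as they are. The removal sentence already carries the recovery criterion of Grade 1 or less, so nothing is lost by taking it out of the first sentence. Sections 7.6 and 8.2 need no change.

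The cost is one sentence in one table cell, with no added visits, tests or analyses. For this trial the change probably only corrects the record; its practical value is where the table is reused in another everolimus protocol.
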